6.5. Study Drug Compliance

The overall compliance (%) for the application of ruxolitinib 1.5% cream BID or vehicle cream BID during the DBVC period will be calculated for all participants in the safety population as follows:

Cream application compliance (%) = $100 \times [\text{total number of nonmissing applications}] / [\text{total number of intended applications}]$, where

Total number of nonmissing applications = number of applications that the participants actually applied during the study, and

Total number of intended applications = $2 \times \text{duration of treatment (days)} - \text{number of interrupted applications}$.

6.6. Prior and Concomitant Medication

Prior medications and concomitant medications will be coded using the WHO Drug Dictionary. The number and percentage of participants with prior and concomitant medication will be summarized by treatment group, as well as overall for the ITT population during the DBVC period by WHO drug class and WHO drug preferred term. For the OLE period, only concomitant medications will be summarized based on OLE evaluable population.

7. EFFICACY

[Appendix A](#) provides a list of data displays. Sample data displays are included in a separate document.

7.1. Efficacy Hypotheses

The primary hypothesis is the superiority of ruxolitinib 1.5% cream BID compared with vehicle cream BID in the proportion of participants achieving IGA-TS at Week 16.

[figure not shown]
7.2. Efficacy Measures

7.2.1. Investigator's Global Assessment

The IGA to assess cutaneous LP has been modified by the sponsor to appropriately assess LP. The investigator/rater will assess the lesions at the study visits by using the descriptors [REDACTED] that best describe the overall appearance of the lesions at a given timepoint. It is not necessary that all characteristics under the morphological description be present.

The IGA-TS is defined as an IGA score of 0 or 1 with \geq 2-grade improvement from baseline. Nonresponder imputation will be used to handle missing postbaseline values in the DBVC period.

[REDACTED] [REDACTED]

7.2.5. Body Surface Area

The total % BSA affected will be estimated at each visit. The BSA assessment will be approximated to the nearest 0.1% using the Palmar Method as a guide, which is the palm plus 5 digits, with fingers tucked together and thumb tucked to the side (handprint) as 1% BSA and the thumb as 0.1% BSA.

7.2.6. Patient-Reported Outcomes

Patient-reported outcomes will be collected and assessed. For all patient-reported outcome assessments conducted at the study site, in order to avoid bias in the participants' responses to the questionnaires, assessments will be completed before any other evaluations or study procedures on the day of the study visit and prior to any treatment-related discussions with the investigator or study site staff.

7.2.6.1. Itch Numerical Rating Scale

The Itch NRS is a daily participant-reported measure (24-hour recall) of the worst level of itch intensity ([Kimball et al 2016](#), [Silverberg et al 2021](#)). Participants will be instructed to complete and record their Itch NRS in a diary each evening beginning on the day of screening through Week 32 or treatment discontinuation, whichever comes first. Participants will rate itch severity of their LP by selecting a number from 0 (no itch) to 10 (worst imaginable itch) that best describes the worst level of itch they experienced in the past 24 hours.

[figure not shown]
The participant's baseline Itch NRS score will be determined by averaging the 7 daily NRS scores before Day 1 (ie, Days -7 to -1) for all the by-visit summaries. The by-visit Itch NRS score for postbaseline visits will be determined by averaging the 7 daily NRS scores before the visit day. If 4 or more daily scores (out of the 7) are missing, the by-visit Itch NRS score will be set to missing. For all daily itch-related analyses, including time to achieve Itch NRS score improvement of at least 4 points analysis, baseline will be defined as the last available Itch NRS score during the week prior to Day 1 (ie, Days -7 to -1). Nonresponder imputation will be used to handle missing postbaseline values in the DBVC period.

[figure not shown]
A participant is said to have an ITCH4 response if they achieved a \geq 4-point improvement in Itch NRS score from baseline. For determining ITCH4 response at a visit, the by-visit Itch NRS score will be compared with the baseline Itch NRS score. For the endpoint time to achieve ITCH4, the daily Itch NRS score will be compared with the baseline Itch NRS score.

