5.1. Inclusion Criteria

Participants are eligible to be included in the study only if all of the following criteria apply:

1. Ability to comprehend and willingness to sign a written ICF for the study.
2. Male or female aged 18 years or older.
3. Clinical diagnosis of LP with predominant cutaneous involvement.
4. IGA score of 3 or 4 at screening and baseline.
5. LP affecting $\leq 20\%$ of the BSA at screening and baseline.
6. Baseline LP-related Itch NRS score ≥ 4 . Baseline Itch NRS is defined as the 7-day average of Itch NRS score before Day 1 (data from a minimum of 4 out of 7 days directly prior to Day 1 is needed).
7. Willingness to avoid pregnancy or fathering children based on the criteria below.
 - a. Male participants with reproductive potential must agree to take appropriate precautions to avoid fathering children from screening through 90 days (a spermatogenesis cycle) after the last application of study treatment and must refrain from donating sperm during this period. Permitted methods in preventing pregnancy (see [Appendix A](#)) should be communicated to the participants and their understanding confirmed.
 - b. Female participants who are WOCBP must have a negative serum pregnancy test at screening and a negative urine pregnancy test before the first study cream application on Day 1 and must agree to take appropriate precautions to avoid pregnancy from screening through 30 days (1 menstrual cycle) after the last application of study treatment and must refrain from donating oocytes during this period. Permitted methods in preventing pregnancy (see [Appendix A](#)) should be communicated to the participants and their understanding confirmed.
 - c. A female participant not considered to be of childbearing potential as defined in [Appendix A](#) is eligible.

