 - c. 2 weeks or 5 half-lives, whichever is longer – strong systemic CYP3A4 inhibitors.
 - d. 2 weeks – systemic antibiotics and immunizations with live-attenuated vaccines, sedating antihistamines unless on a long-term stable regimen (nonsedating antihistamines are permitted).
 - e. *Note:* Live-attenuated vaccines are prohibited during the DBVC period. COVID-19 vaccination is permitted.
 - f. 2 weeks – treatment with topical therapy (eg, topical corticosteroids, pimecrolimus, and tacrolimus).
5. Current treatment or treatment within 30 days or 5 half-lives (whichever is longer) before the baseline visit with another investigational medication or current enrollment in another investigational drug protocol.
6. Pregnant or lactating participants, or those considering pregnancy during the period of their study participation.
7. History of alcoholism or drug addiction within 1 year before screening or current alcohol or drug use that, in the opinion of the investigator, will interfere with the participant's ability to comply with the administration schedule and study assessments.

8. Previous treatment with systemic or topical JAK inhibitors (eg, ruxolitinib, tofacitinib, baricitinib, filgotinib, lesartanib, pacritinib).
9. Inadequate venous access in nonlesional areas or in areas not treated by the study drug.
10. Known allergy or reaction to any of the components of the study drug.
11. In the opinion of the investigator, are unable or unlikely to comply with the administration schedule and study evaluations.
12. Committed to a mental health institution by virtue of an order issued either by the judicial or the administrative authorities.
13. Employees of the sponsor or investigator or otherwise dependents of them.

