8.2.8. Patient-Reported Outcomes

Patient-reported outcomes will be collected and assessed as outlined in the SoA (see [Table 3](#)). For all patient-reported outcome assessments conducted at the study site, in order to avoid bias in the participants' responses to the questionnaires, assessments should be completed before any other evaluations or study procedures on the day of the study visit and prior to treatment-related discussions with the investigator or study site staff.

8.2.8.1. eDiary Assessments

The participant will be instructed to complete and record their Itch NRS and Skin Pain NRS scores via eDiary every evening beginning on the day of screening through Week 32 or ET.

Both the Itch NRS and Skin Pain NRS are a daily participant-reported measure (24-hour recall) of the worst level of itch or skin pain intensity related to LP.

The participants will rate the following:

- Itch NRS: Itch severity of their LP by selecting a number from 0 (no itch) to 10 (worst imaginable itch) that best describes their worst level of itching in the past 24 hours.
- Skin Pain NRS: Pain severity of their LP by selecting a number from 0 (no pain) to 10 (worst imaginable pain) that best describes their worst level of pain in the past 24 hours.

The average of the 7-day Itch NRS score prior to the baseline visit (minimum 4 out of 7 days' data required) will be used to determine if a participant meets the inclusion criteria.

Detailed directions for the administration of the eDiary will be provided in the Study Manual.

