10.4.2. Secondary Analysis

All secondary [REDACTED] efficacy variables will be summarized using descriptive statistics based on the ITT population. For categorical measurements, summary statistics will include sample size, frequency, and percentages. For continuous measurements, summary statistics will include sample size, mean, median, STD, standard error of the mean, minimum, and maximum. Summary statistics for continuous measures will be provided for baseline, the actual measurements at each visit, and the change and percentage change from baseline at each visit, if applicable. The Itch NRS score as well as the Skin Pain NRS score for each visit will be determined by averaging the 7 daily scores for Itch or Skin Pain before the corresponding visit day. If 4 or more daily scores are missing (out of the 7), the Itch NRS or Skin Pain NRS score at the visit will be set to missing.

For the time to achieve ITCH4, a log-rank test stratified by randomization stratification factor will be used for between-treatment group comparisons. The hazard ratio and its 95% CI will be estimated based on the stratified Cox regression model using Efron's method accounting for ties. Kaplan-Meier curves will be presented by treatment groups. The number of participants, number of events, and number of censorings will be summarized by treatment groups. The Kaplan-Meier estimate of median time will be presented with its 95% CI. The 95% CI will be calculated using the method by Brookmeyer and Crowley (1982).

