7.4.3. Time-To-Event Efficacy Endpoint

The time to achieve Itch NRS score improvement of at least 4 points from baseline (ie, ITCH4) will use the daily Itch NRS score in comparison to baseline Itch NRS score in the DBVC period. A log-rank test stratified by randomization stratification factor, baseline IGA score (3 or 4), will be used for between-treatment group comparisons. The hazard ratio and its 95% CI will be estimated based on the stratified Cox regression model using Efron's method accounting for ties. Kaplan-Meier curves will be presented by treatment groups. The number of participants, number of participants with events, and number of participants censored will be summarized by treatment group. The Kaplan-Meier estimate of median time will be presented with its 95% CI. The 95% CI will be calculated using the method by Brookmeyer and Crowley (1982).

The last available value for time to ITCH4 during the DBVC period is the last nonmissing measurement obtained after the first application of study cream and within 30 days after the last application of study cream in DBVC period, or before the first application of study cream in the OLE period, whichever is earlier.

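### Time to ITCH4 is measured from one last diary score, while by-visit ITCH4 and eligibility use the 7-day average; if daily scores are noisy this lowers log-rank power, and a few eligible participants cannot have the event

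*SAP*

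**What the plan says.** SAP 7.2.6.1 defines two Itch NRS baselines. One is obtained "by averaging the 7 daily NRS scores before Day 1 (ie, Days -7 to -1) for all the by-visit summaries", and by-visit ITCH4 is judged against it. For every daily itch analysis, time to ITCH4 included, "baseline will be defined as the last available Itch NRS score during the week prior to Day 1". SAP 7.4.3 does not repeat the distinction; it says only that the endpoint "will use the daily Itch NRS score in comparison to baseline Itch NRS score in the DBVC period".

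The protocol uses the average for eligibility. Criterion 6 of Protocol 5.1 requires a score of at least 4 and states: "Baseline Itch NRS is defined as the 7-day average of Itch NRS score before Day 1", with at least 4 of the 7 days present. Protocol 8.2.8.1 repeats this. Protocol 10.4.2 sets out the stratified log-rank test and Cox model for time to ITCH4 but names no baseline. In the readable text, neither document gives a reason for the second baseline or a rule for a participant whose last score is below 4.

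**The concern.** The same label, ITCH4, is judged against two references. Two things follow.

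- **Misplaced thresholds (the main effect).** A single score carries a full day's error. If the last day happens to be high, a 4-point fall comes too easily; if it is low, it comes too hard or not at all. The error stays with the participant for the whole DBVC period and blurs the difference between arms.
- **Impossible events (the smaller effect).** The scale runs in whole numbers from 0 to 10, so a last score of 0 to 3 cannot fall by 4. Such a participant stays in the risk set and can still be a by-visit ITCH4 responder.

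Time to ITCH4 is a named secondary endpoint with a planned p-value and hazard ratio. What is at stake is an understated or missed itch effect, not a false claim of benefit.

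**Working it through.** **1. The plan's own figure.** The documents state no power, event count or hazard ratio for time to ITCH4. The only power statement is above 80% for IGA-TS (58% vs 20%, Fisher exact, 2-sided 0.05). Exact enumeration at 30 per arm gives 81.0%, so it reproduces. It does not bear on this endpoint.

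**2. Impossible event, by arithmetic.** Take daily scores 5, 5, 5, 5, 5, 5, 3.
- Average = 33/7 = 4.71, so the participant is eligible.
- By-visit response needs a visit average of at most 4.71 - 4 = 0.71, which is possible.
- Time to ITCH4 starts from 3. The largest fall is 3 - 0 = 3, so no event is possible.

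With the average as baseline this cannot happen. Every eligible baseline is at least 4, and a 7-day mean at least 4 below baseline needs at least one day at least 4 below it.

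**3. Threshold error, without assuming its size.** Let daily error have SD s and lag-1 autocorrelation r, in a stable baseline week. The last score has error SD s. The 7-day mean has variance (s²/49) × [7 + 2 Σ (7 - k) r^k], k = 1 to 6:
- r = 0: 7/49 = 0.143, SD 0.38s
- r = 0.4: 14.1/49 = 0.288, SD 0.54s
- r = 0.9: 39.1/49 = 0.798, SD 0.89s

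**4. Power, by simulation.**
- From the documents: 30 per arm, 112 days, integer scores 0 to 10, entry if the 7-day mean is at least 4, event on the first day at least 4 below baseline, log-rank test stratified by baseline IGA.
- Assumed: 30% with IGA 4; person mean itch 6.7 or 5.5 (SD 1.6); autoregressive daily error; no missing diaries or dropout. Three effect patterns (mean fall, active vs vehicle): A 3.5 vs 1.5, between-person SD 2, time constant 21 days; B 4.5 vs 1.5, SD 2, 10 days; C 3.5 vs 2.0, SD 1, 21 days.
- 2,000 replicates per setting, Monte Carlo SE at most 1.1 points.

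Pattern A, mean 6.7, stable baseline week; power (%) with last score / average:

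| Autocorrelation | SD 0.5 | SD 1.0 | SD 1.5 | SD 2.0 |
|---|---|---|---|---|
| 0 | 86.0 / 87.9 | 73.0 / 87.2 | 36.6 / 72.4 | 16.7 / 47.8 |
| 0.4 | 86.9 / 87.2 | 73.4 / 84.6 | 39.8 / 71.3 | 17.1 / 42.8 |
| 0.9 | 84.7 / 84.3 | 75.5 / 79.0 | 59.4 / 65.4 | 39.3 / 50.3 |

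Over all 18 stable-week settings per SD (three patterns, three autocorrelations, two means), the last score loses -0.4 to 1.9 points at SD 0.5, about 1 to 30 at SD 1.0, 3 to 52 at SD 1.5 and 11 to 59 at SD 2.0. A separately coded simulation with other assumptions (falls 4.0 vs 1.5, autocorrelation 0.5) shows the same pattern: 97 vs 97, 86 vs 95, 47 vs 78 and 20 vs 49%.

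**5. Itch changing over Days -7 to -1.** Itch could rise, because topical therapy stops 2 weeks before baseline (Protocol 5.2). Pattern A:
- Rise of 1.5 points: the average is about 4 to 9 points worse at SD 0.5. At SD 1.0 it is level with autocorrelation 0.9 (76.7 vs 77.1) and 11 to 15 points better with autocorrelation 0 to 0.4. At SD 1.5 it is 7 to 45 points better.
- Rise of 0.75 points, SD 0.5: the average is 1 to 4 points worse.
- Fall of 1.5 points: the average is better in all 12 settings, by 2 to 26 points.

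**6. How many cannot have the event.** At autocorrelation 0.4 and SD 0.5, 1.0, 1.5 and 2.0, the share with a last score below 4 is 0.3, 1.7, 4.1 and 7.1% at mean 6.7, and 0.7, 4.1, 8.0 and 11.9% at mean 5.5. The maximum over all settings is 13.0%, or about 8 of 60.

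**7. Which effect dominates.** Repairing only the impossible events (pattern A, autocorrelation 0.4) moves power from 74.1 to 77.1, against 85.9 with the average, at SD 1.0; from 39.5 to 47.6, against 68.7, at SD 1.5; and from 17.5 to 26.2, against 43.4, at SD 2.0. That recovers 3.0/11.8 = 25%, 8.1/29.2 = 28% and 8.7/25.9 = 34% of the loss. The rest comes from misplaced thresholds.

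**8. Type I error.** With both arms falling 1.5 points, rejection is 4.6 to 6.3% with the last score and 3.8 to 6.5% with the average. Neither is materially inflated.

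**The case against.** The strongest reply is that this is a stated choice. The SAP pairs week mean with week mean and single day with single day, follows its own last-value convention (SAP 4.1.3), and contradicts nothing in Protocol 10.4.2. That is right, and no breach is alleged. But a like-for-like pairing does not make a one-day threshold precise, and the SAP already leaves that convention for by-visit itch and Skin Pain.

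The size is assumed. This stands: at SD 0.5 with a stable week nothing is lost, and with autocorrelation 0.9 the pattern A loss is 3.5 points at SD 1.0 and 6.0 at SD 1.5. With rising itch and little noise the average is worse.

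A single unconfirmed day still triggers the event after the change. This also stands. With no true change, SD 2.0 and autocorrelation 0.4, 79% record an event with the average, 76% with the last score and 7% if the event uses a trailing 7-day mean.

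By-visit ITCH4, including the stratified Week 16 test in SAP 7.4.2, already uses the average, so an itch effect has another route to being seen. That limits the consequence.

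The change needs 4 of 7 scores, where the last-score rule needs one. Eligibility already requires 4 of 7 and Protocol 5 allows no waivers, so only an eligibility deviation would be affected.

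Finally, parts of the itch text and outputs are blacked out, so an average-baseline version may already exist there.

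**Conclusion.** The concern holds, as a minor one. Two parts need no assumption about diary noise: the two baselines differ, and an eligible participant with a last score of 0 to 3 cannot have the event. The loss of power is conditional on noise. It is about nil at daily SD 0.5 in a stable week and grows from about SD 1.0 upward, least when scores persist strongly from day to day. In the central case (falls 3.5 vs 1.5, autocorrelation 0.4) it is about 11 points at SD 1.0 and 32 at SD 1.5. The true size is unknown because the documents give no diary SD, autocorrelation or itch effect. The exception is itch rising before Day 1 with very little noise. The effect is confined to one secondary endpoint; alpha is set only for the primary analysis, and IGA-TS and the Week 16 ITCH4 test do not change.

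**What to change.** Before the primary database lock and unblinding, amend SAP 7.2.6.1 and 7.4.3:

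- Define baseline for time to ITCH4 as the average over Days -7 to -1, with at least 4 of 7 scores, and say how a participant with fewer is handled.
- Keep the last-score version as a sensitivity analysis. It also covers itch rising before Day 1.
- Report by arm how many participants have a last score below 4.
- State which baseline any other daily itch change analysis uses, since the present sentence covers all of them.
- Optionally, add a supportive analysis whose event is the first day on which the trailing 7-day mean (at least 4 scores) is at least 4 below the average baseline. In pattern A with autocorrelation 0.4 and a stable week, its power is 83.0, 83.4, 82.0 and 74.8% at SD 0.5, 1.0, 1.5 and 2.0.

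If a blacked-out section already has an average-baseline version, only the choice of main analysis needs stating.

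The cost is one sentence, a cross-reference and one or two outputs. No new data are needed, because the average is already derived. There are three downsides. At SD 0.5 with itch rising 1.5 points, about 4 to 9 points of power are lost. Whole-number scores against a fractional average require a fall of 4.0 to 4.86 points, which the power figures already include. The optional trailing mean, against the last score at SD 0.5, costs about 3 to 4 points in a stable week and 11 to 15 with itch rising 1.5 points.

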7.2.6.2. Skin Pain Numerical Rating Scale

Participants will be instructed to complete and record the Skin Pain NRS in a diary each evening beginning on the day of screening through Week 32 or treatment discontinuation. Participants will rate their pain, which will include all types of pain (eg, burning, tearing, pulling, stabbing, etc) severity of the LP by selecting a number from 0 (no pain) to 10 (worst imaginable pain) that best describes the worst level of pain they experienced in the past 24 hours.

The participant's baseline Skin Pain NRS score will be determined by averaging the 7 daily NRS scores before Day 1 (ie, Days -7 to -1). The by-visit Skin Pain NRS score for postbaseline visits will be determined by averaging the 7 daily NRS scores before the visit day. If 4 or more daily scores (out of the 7) are missing, the Skin Pain NRS score at the visit will be set to missing. No imputation will be performed for missing values.

7.3. Analysis of the Primary Efficacy Parameter

7.3.1. Primary Efficacy Analysis

The primary efficacy analysis will be based on the ITT population. The primary efficacy endpoint is the IGA-TS response, defined as an IGA score of 0 or 1 with \geq 2-grade improvement from baseline, at Week 16. The comparison of the proportions of participants achieving IGA-TS at Week 16 will be made between the ruxolitinib 1.5% cream BID arm and the vehicle cream BID arm. The primary hypothesis (the superiority of ruxolitinib 1.5% cream BID compared with vehicle cream BID in participants with cutaneous LP) will be tested using a Cochran-Mantel-Haenszel test stratified by baseline IGA score (3 or 4) at a 2-sided $\alpha = 0.05$ level. The p-value and stratum-adjusted IGA-TS response rate difference with 95% CI will be provided. A summary of IGA-TS rates will be reported for each treatment group. Nonresponder imputation will be used to handle missing postbaseline values in the DBVC period.

